### 10.2.3 Other Baseline Procedures

Any subject questionnaire should be completed by the subject in a private setting after receiving instruction from research personnel. The Research Coordinator should review questionnaires for completeness prior to enrolment. If a question is left unanswered or is uninterpretable, the coordinator should return the questionnaire to the subject, requesting that subject complete the missed or equivocal question(s).

**Table 6** summarises the pre-procedure activities not intended to screen for eligibility, but pertain to patient risk, confounding factors, and obtaining baseline health status.

**Table 6 Pre-Procedure Activities\***

*Includes data collection and procedures that don't determine eligibility		
Activity	Considerations and instructions	Time Frame
Sexual Function Questionnaire	
 
• A baseline SHIM should be completed if patients are sexually active within the previous 6 months.
 
	
 
• Recall period of 6 months; complete in screening as applicable.
 

Urodynamics	
 
• Determine the grade of bladder outlet obstruction (BOO) and to assess detrusor contractility function
 
	
 
• During screening, after consent, within 30 days of index procedure.
 
• Urodynamics testing may be performed at each study site if a testing facility is available and a qualified operator is on-site.
 

Medications	
 
• BPH, LUTS; Sexual Function; GU; should be captured.
 
	
 
• Collect through 10 years history of non-transient prescriptions with approximate duration and indication.
 

Alpha Blocker	
 
• It is required that subject was on alpha blocker at a minimum, through previous failed TWOC.
 
	
 
• Alpha blockers should be prescribed per site's standard of care throughout the duration of the study. Initiation and cessation should be documented on the concomitant medication log.
 

Aspirin	
 
• If patient on regular dose <math>\leq</math> 100 mg no washout required.
 
• If patient takes PRN, instruct patient to avoid.
 
	
 
• 3 days prior to index procedure
 

Anticoagulants	
 
• Patient should be cleared to washout or, excluded.
 
	
 
• 3 days prior to procedure
 

Catheter use	
 
• Record history, type, duration, indication, of catheter, reason out
 
	
 
• Most recent
 

### 10.3 Enrolment

A subject is considered enroled if he has signed the approved informed consent form to participate in the study, has met all inclusion and exclusion criteria, and the first UroLift delivery device has been inserted. Once subject is enroled, adverse events need to be documented and reported.

#### 10.3.1 UroLift System Procedure Instructions

The UroLift System procedure may be performed in the office setting, ambulatory surgical centre, or hospital utilising appropriate level of anaesthesia and sedation per institutional standards.

Antibiotic therapy will be initiated on or prior to procedure day with the type of antibiotic and duration identified per institutional standards (e.g. a five day course of oral ciprofloxacin). The use of these agents will be recorded on the case report forms.

A pre-procedure cystoscopic visualisation should also be performed if not previously captured and recorded. Cystoscopy should include visualisation of full prostatic urethra and bladder neck and to plan implant placement. The cystoscopy and procedure recorded file should be de-identified and provided to NeoTract.

### 10.3.2 UroLift System Equipment

Per the Instructions for Use (IFU), the following ancillary equipment will be used:

1. 2.9 mm 0° telescope (i.e. NeoTract REF UL-SCOPE, Storz REF 10324AA, or equivalent)
2. 20F sheath (NeoTract REF UL-SHEATH, Storz REF 27026C, or equivalent)
3. Visual obturator (NeoTract REF UL-VO, Storz REF 27028CN, or equivalent)

The following equipment (“Retrieval Kit”) should be used if desired or necessary to retrieve or remove part of the UroLift Implant during the procedure.

1. 4 mm 30° telescope (UL-SCOPE4 or equivalent)
2. Telescope bridge (UL-WBRIDGE or equivalent)
3. Endoscopic rigid grasper or rigid scissors

Facility equipment should include:

1. Cystoscopy camera, light box/cable and monitor, with video recording capability
2. Standard fluid irrigation system including new, sterile fluid tubing

All of the ancillary equipment, including the telescope, sheath, visual obturator, bridge and graspers must be sterilised per the respective manufacturer’s instructions before and after use.

NeoTract will loan needed ancillary equipment as needed to study facilities throughout the enrolment period.

### 10.3.3 Training in Prostatic Urethral Lift Procedure

Selected Principal Investigators in the study will have performed a minimum of 30 UroLift procedures. Each will have undergone the NeoTract Professional Education Program.

### 10.3.4 Post Procedure Instructions

After creating an unobstructed anterior channel, continue with cystoscopy to verify implants are not present in the bladder, or extending into the bladder vesical. Interrogate the bladder neck for protruding implants. If a protruding or exposed implant is present, it should be removed.

A urinary catheter will be placed prophylactically after the Investigator completes the UroLift procedure, and subject provided instructions on its proper maintenance. The subject should remain on

alpha blockers per the site's standard of care. Initiation and cessation should be documented on the concomitant medication log. A post-procedure follow-up visit to perform Trial without Catheter will be scheduled for 3 days ( $\pm 1$  day) after index procedure.

The Investigator or designee will record the following procedural data:

- Device: number of UroLift devices used, location of implantation, lot number, performance
- Cystoscopy findings, including confirmation of inclusion criteria, stones, and other notable pathology
- Time: subject enters and leaves procedure room, first/last UroLift device, catheter placement
- Anaesthesia/sedation: duration, type, and delivery of procedural medications
- Clinical staff required during the procedure
- Complications/adverse events
- Venue type (clinic, outpatient, inpatient, etc.)
- Time to discharge or release from treatment facility
- Urinary catheter placement, type and timing (length)
- Medications used
- Post-operative interventions (if any)

#### 10.4 Post-Procedure Trial Without Catheter (TWOC)

The subject will return to clinic **3 days ( $\pm 1$  day)** after Index procedure for the primary study assessment screening of bladder function without catheter. TWOC will be considered successful if the spontaneous void is  $\geq 100$  mL with PVR  $< 300$  mL. If subject fails the initial TWOC, at least one additional TWOC will be performed per standard of care. All catheterisations will be recorded on the eCRF.

The following evaluations will be performed in office **3 days ( $\pm 1$  day)** after index procedure in conjunction with the TWOC:

- Relevant Concomitant medications: BPH/LUTS; Sexual Function; GU; Prostate Cancer
- Freestanding uroflow and post void residual (PVR)
- Catheterisation review
- Adverse Event review; Intervention review

#### 10.5 6 Week Follow-up Procedures

The following evaluations will be performed in office **6 Weeks ( $\pm 7$  days)** after index procedure:

- Questionnaires to be completed by the subject:

- Urinary Symptoms questionnaires including IPSS & QoL (International Prostate Symptoms Score with Quality of Life) and BPHII (Benign Prostatic Hyperplasia Impact Index) unless current indwelling catheter.
- SHIM (Sexual Health Inventory for Men): Recall period for this visit should cover only post-enrolment activity. Completed if subject was sexually active at baseline.
- Return to Normal
- Patient Satisfaction
- Symptom questionnaire upon occurrence (includes: Incontinence Severity Index (ISI), haematuria, dysuria, pelvic pain VAS)
- Relevant Concomitant medications: BPH/LUTS; Sexual Function; GU; Prostate Cancer
- Urinalysis (urine culture and sensitivity if abnormal, clinically significant and indicates a urinary infection). UA not required if current indwelling catheter.
- Freestanding uroflow and post void residual (PVR)
- Voiding Assessment
- Catheterisation Review
- Adverse Event Review; Intervention Review

## 10.6 3 Month Follow-up Procedures

---

The following evaluations will be performed in office at **3 months (± 14 days)** post procedure:

- Questionnaires to be completed by the subject:
  - Urinary Symptoms questionnaires including IPSS & QoL (International Prostate Symptoms Score with Quality of Life) and BPHII (Benign Prostatic Hyperplasia Impact Index) unless current indwelling catheter.
  - SHIM (Sexual Health Inventory for Men): Recall period since the last visit or 6 week follow-up. Completed if subject was sexually active at baseline.
  - Return to normal if not already achieved
  - Patient Satisfaction
  - Symptom questionnaire upon occurrence (includes: Incontinence Severity Index (ISI), haematuria, dysuria, pelvic pain VAS)
- Relevant Concomitant medications: BPH/LUTS; Sexual Function; GU; Prostate Cancer
- Urinalysis (urine culture and sensitivity if abnormal, clinically significant and indicates a urinary infection). UA not required if current indwelling catheter.
- Freestanding uroflow and post void residual (PVR)
- Digital Rectal Exam (DRE)
- Voiding Assessment
- Catheterisation review

- Adverse Event review; Intervention Review

## 10.7 6 Month Follow-up Procedures

The following evaluations will be performed by telephone, unless Investigator elects to perform in office, at **6 months (± 14 days)** post index procedure:

- Telephone administration of subject questionnaires:
  - Urinary Symptoms questionnaires including IPSS & QoL (International Prostate Symptoms Score with Quality of Life) and BPHII (Benign Prostatic Hyperplasia Impact Index) unless current indwelling catheter.
  - Patient Satisfaction
  - Symptom questionnaires upon occurrence (includes: Incontinence Severity Index (ISI), haematuria, dysuria, pelvic pain VAS)
- Relevant Concomitant medications: BPH/LUTS; Sexual Function; GU; Prostate Cancer
- Voiding Assessment
- Catheterisation review
- Adverse Event review; Intervention review

## 10.8 12 Month Follow-up Procedures

The following evaluations will be performed at **12 months (± 30 days)** post index procedure:

- If subject is scheduled for or has already undergone alternative surgical procedure, see also section **10.10.1**.
- Questionnaires to be completed by the subject:
  - Urinary Symptoms questionnaires including IPSS & QoL (International Prostate Symptoms Score with Quality of Life) and BPHII (Benign Prostatic Hyperplasia Impact Index) unless current indwelling catheter.
  - SHIM (Sexual Health Inventory for Men): Recall over the last 6 months. Completed if subject was sexually active at baseline.
  - Patient Satisfaction
  - Symptom questionnaires upon occurrence (includes: Incontinence Severity Index (ISI), haematuria, dysuria, pelvic pain VAS).
- Relevant Concomitant medications: BPH/LUTS; Sexual Function; GU; Prostate Cancer
- Freestanding uroflow and post void residual (PVR) unless current indwelling catheter or adverse event does not permit.
- Urinalysis (urine culture and sensitivity if abnormal, clinically significant and indicates a urinary infection). UA not required if current indwelling catheter.
- Digital Rectal Exam (DRE)
- Urodynamics testing, if applicable to site

- Cystoscopy (flexible)
- Voiding Assessment
- Catheterisation Review
- Adverse Event Review; Intervention Review

## 10.9 Interim Visits

Testing or procedures performed for adverse events associated with BPH or LUTS should be recorded and entered into eCRFs throughout the duration of subject follow-up even if outside protocol visit windows.

## 10.10 Surgical Intervention

The following information will be collected in association with secondary interventions:

- Adverse Event leading to the intervention (Unless urinary retention- **See Section 14.3**)
- Date of procedure
- Type(s) of procedure(s) performed
- Pre-procedure diagnosis for undergoing procedure
- Complications (as Adverse Events)
- Count of UroLift implant removal(s) and placements, if applicable
- Catheterisation use

### 10.10.1 Alternative Surgical Intervention

A subject with recurring urinary retention requiring catheter or other LUTS may require alternative surgical intervention (HoLEP, TURP, PVP, etc). The subject will remain in study through 12 months with the following abbreviated requirements:

- 1) Upon the surgery scheduling, study visits will no longer be required with the exception of the 12 month visit.
  - a. If subject is on catheter during the final visit (12 month) the urinalysis and urinary symptoms will not be required. Ongoing adverse events and catheterizations will be required. Refer to **Table 7**, Schedule of Procedures.
- 2) Between reintervention and 12 month visit, only urological serious adverse events (SAE) should be reported.

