**Table 2 Definitions**

Adverse event (AE)	An adverse event (AE) is defined as any undesirable medical occurrence in a clinical trial subject, whether it is considered to be related to the device or not, that includes a clinical sign, symptom, or condition.  Once a subject is enroled, all AEs must be reported through follow-up period. Only exacerbated conditions or new onset qualify as an AE. Principal Investigator will assess severity, relatedness, serious or unexpected.
Alternative Surgical Intervention	A post-index procedure surgery, other than PUL, to treat BPH.
Acute Urinary Retention	Painful inability to void and a residual volume < 1500 mL.
Invasive BPH surgery	
 
• Transurethral resection of the prostate (TURP)
 
• Transurethral Laser (PVP, HoLEP or Interstitial)
 
• Open Prostatectomy
 

Index procedure	The first procedure to which subjects are enroled.
Precipitated AR	Acute urinary retention that develops in response to a trigger such as UTI, anaesthesia, surgery, medications with sympathomimetic or anticholinergic effects.
Serious Adverse Event (SAE)	
Serious Adverse Event (SAE) is defined as untoward occurrence that: (a) results in death; (b) is life-threatening; (c) requires hospitalisation or prolongation of existing hospitalisation (d) results in persistent or significant disability or incapacity; (e) consists of a congenital anomaly or birth defect; or (f) is otherwise considered medically significant by the investigator.
 
(in-patient hospitalisation is at least 24 consecutive hours)

Unexpected Adverse Event	An unexpected adverse event is an event which by nature, incidence, severity or outcome has not been identified in the current version of the Sponsor risk management files.
Spontaneous AR	Associated with older age, BPH, elevated PSA, or presence of severe LUTS.
PUL Procedure Time	Time from first device insertion to last device removed.

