#### 10.10.2 Secondary PUL

A subject undergoing a procedure for UroLift implant removal (misplaced) or additional implant(s) placement will remain on their original follow-up visit schedule.

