## 14.5 Adverse Event Reporting

Adverse events will be collected on all enroled subjects. Subjects will be asked about adverse events at each visit, and all AEs will be documented and reported regardless of relatedness.

Adverse events will be documented on the AE electronic case report form (eCRF) within the study's Electronic Data Capture System (EDC).

When an SAE occurs, the Sponsor should be notified within 24 hours of site awareness via completion of the AE eCRF in the EDC System. Sponsor will receive an alert upon any SAE entry and will be responsible for reporting to notified body, ethics committee and all other participating investigators as applicable. Should Sponsor determine, either through investigator reports or in-house testing, that a unexpected SAE presents an unreasonable risk to all participating subjects, Sponsor will suspend the clinical investigation.

It is the responsibility of the Chief Principal Investigator to report all related and unexpected Serious Adverse Events (SAEs) to the ethics committee. The Sponsor may report on behalf of the Chief Investigator. Device-related SAEs in this study, using a CE-marked device in a post-market surveillance study, are reportable to the MHRA Adverse Incident Centre as reported under the requirements of the Devices Vigilance requirement.

Annual and final reports will be provided to the EC as applicable per EC requirements with Sponsor assistance.

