## 16 Study Data Analysis

---

All effectiveness analyses will be performed on the “intent-to-treat (ITT)” group. All subjects who were enroled with at least one UroLift device introduced will be included in the intention to treat analysis. Effectiveness assessments for enroled subjects whom later undergo surgical retreatment with either PUL or with any other surgical procedure will be censored the day after the secondary intervention. Censoring in adverse event analysis will be applied only to alternative surgical retreatments and not to secondary PUL.

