### 16.3 Safety Population

---

The safety population will be used for all safety assessments. The safety population includes all enroled subjects with at least one UroLift device introduced. Safety assessments for enroled subjects whom later undergo surgical retreatment with any other surgical procedure will be censored on the day of the secondary intervention. Censoring in adverse event analysis will be applied only to alternative surgical retreatments and not to secondary PUL.

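### Section 10.10.1 waives visits from an undefined surgery-scheduling event, but safety is censored only at surgery, so scheduled AE, catheterisation and intervention reviews lapse in men still at risk

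*Combined protocol and SAP*

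**What the plan says.** Section 10.10.1 sets reduced requirements for a man who is to have alternative surgery. Item 1 reads: "Upon the surgery scheduling, study visits will no longer be required with the exception of the 12 month visit". Item 1(a), which concerns a man on a catheter at the final visit, adds: "Ongoing adverse events and catheterizations will be required". Item 2 reads: "Between reintervention and 12 month visit, only urological serious adverse events (SAE) should be reported". By contrast, section 10.10.2 says that men who have a secondary PUL "will remain on their original follow-up visit schedule".

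The analysis rules use a different date. Under section 16.3, safety assessments in men who have alternative surgery "will be censored on the day of the secondary intervention". Under section 16, effectiveness assessments after any surgical retreatment "will be censored the day after the secondary intervention".

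On reporting, Table 2 says: "Once a subject is enroled, all AEs must be reported through follow-up period". Section 14.4 likewise requires every AE after enrolment to be entered in the eCRF. Section 14.5 says how events are sought: "Subjects will be asked about adverse events at each visit". Table 7 lists the AE, catheterisation and intervention reviews by visit.

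**The concern.** The visit waiver and the censoring rule start from different events. Between scheduling and surgery a man stays in the safety and effectiveness analyses, but the contacts at which he would be asked about events, catheters and interventions are waived. This happens only to men for whom PUL appears to have failed and who are heading for alternative surgery. Active ascertainment is therefore thinnest in the group where the study most needs to know what happened. The continuing duty to report AEs does not cover recurrent retention, because section 14.3 says that this is not an AE.

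The trigger is also loose. Scheduling does not appear in Table 2, and the list in section 10.10 asks for the procedure date but no scheduling date. Sites could start the waiver at different points, and nobody could later reconstruct when it began. Section 7 gives this study the task of settling methodology for a larger trial, so an unclear rule could carry forward.

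**Working it through.** The documents state no figure on this point, so there is none to reproduce. The check has two parts.

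**What continues and what lapses during the wait**

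- AE reporting continues. Table 2 and sections 14.4 and 14.5 require all AEs, and item 2 of section 10.10.1 narrows this only from reintervention.
- Some catheter and intervention data continue. Section 10.4 has all catheterisations recorded. Section 10.10 collects, with the surgery, its date, complications, catheter use and the AE that led to it (unless that was urinary retention). Section 10.9 has testing for BPH or LUTS events entered even outside visit windows.
- Scheduled questioning lapses. Table 7 and section 14.5 attach it to visits, and item 1 removes the visits.
- Item 1(a) might be read as keeping AE and catheter review throughout, but it sits under the 12-month sub-item. Whether it covers the wait is unclear.

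**How long the gap could be**

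Inputs: visits on nominal days 42, 91 and 182 (6 weeks, 3 months, 6 months); month 12 taken as day 365; safety window of 91 days. Scheduling days of 4, 14, 42 and 91 are assumed. Waits of 4 and 12 weeks are assumed. The 30 weeks is the average wait in section 6, which counts it from counselling and describes men before any PUL; applying it from scheduling is an assumption.

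Formulas: surgery day = scheduling day + 7 × weeks of wait. A review is lost if its day falls after scheduling and before surgery. Uncovered days = the smaller of 91 and the surgery day, minus the scheduling day.

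| Wait | Day 4 | Day 14 | Day 42 | Day 91 |
|---|---|---|---|---|
| 4 weeks | none; 28 days | none; 28 | none; 28 | none; 0 |
| 12 weeks | 6 wk; 84 | 6 wk, 3 mo; 77 | 3 mo; 49 | none; 0 |
| 30 weeks | all three; 87 | all three; 77 | 3 mo, 6 mo; 49 | 6 mo; 0 |

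Example: scheduling on day 14 with a 30-week wait gives surgery on day 14 + 210 = 224. Days 42, 91 and 182 all fall before it, and 91 − 14 = 77 days of the safety window have no required visit.

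The 4-week row shows no loss on the days tested. On other days one review can be lost: scheduling on day 30 gives surgery on day 58, which spans day 42. It cannot be two, because the visits are 91 − 42 = 49 and 182 − 91 = 91 days apart, both more than 28.

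Delay in that 30-week, day-14 example, for an AE starting on day 14 to 90:

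- Under the waiver, the next scheduled question is at month 12: 365 − 90 = 275 to 365 − 14 = 351 days later.
- Under the full schedule, onset on days 14 to 42 waits 42 − 14 = 28 down to 0 days. Onset on days 43 to 90 waits 91 − 43 = 48 down to 91 − 90 = 1 day. The range is 0 to 48 days.

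These delays concern scheduled questioning. Spontaneous reports, interim contacts and the data collected with the surgery may bring an event to light sooner.

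**The case against.** The strongest reply is that little is lost. All AEs remain reportable, SAEs must reach the sponsor within 24 hours of site awareness, catheter use is collected with the surgery, and the 12-month visit keeps all three reviews. A reader might infer that the protocol suspends AE reporting during the wait. It does not: item 2 of section 10.10.1 limits reporting only after reintervention. This part of the reply stands and confines the point to scheduled questioning.

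A second reply is that scheduling most naturally means a booked theatre date. Section 10.11 uses a separate term, prescribed surgery, for the decision to operate. On that reading the gap may be short and the loss small or nil. This is plausible, but no definition settles it. Section 10.8 provides for a man who at month 12 is scheduled but not yet operated on, so the protocol itself allows for waits that reach month 12.

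Third, the waiver is deliberate, the study has no formal success criteria (section 16.7), and the comparison with the retrospective arm is not powered (section 16.6). That is fair, and it limits the severity. It does not explain why the waiver and the censoring rule start on different dates.

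Other inferences should be resisted:

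- A lost Clavien-Dindo grade does not follow. Section 14.6 ties grading to onset within 90 days and completes adjudication before the final report, so an event found late can still be graded.
- A distorted Kaplan-Meier estimate of freedom from alternative surgery does not follow. The 12-month visit is retained, so a man without surgery who attends is censored there.
- A net bias against the surgical arm does not follow. Section 15.8.3 collects that arm's post-surgery data only where available.

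**Conclusion.** The concern holds as a minor point. From an undefined and unrecorded scheduling event until the alternative surgery, the plan counts a man as at risk but does not clearly require the scheduled AE, catheterisation and intervention reviews. Men who have a secondary PUL are not affected.

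The size cannot be fixed from the documents, which give no failure rate, scheduling rate or gap length. It runs from no lost review to all three before month 12; the upper end rests on early scheduling and the assumed 30-week gap. No number of missed AEs is claimed, because any such figure would only restate assumed rates. The effect on the 3-month related-SAE rate may be zero. The day-3 voiding trial, which precedes almost all of this, is essentially unaffected. No direction of bias is claimed.

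**What to change.** In section 10.10.1, item 1:

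- Define scheduling as one dated event and record that date in the eCRF.
- State that after this date clinic tests and questionnaires are no longer required before month 12, but that the AE, catheterisation and intervention reviews at 6 weeks, 3 months and 6 months remain required, by telephone if preferred, until the date of the alternative surgery. This also settles whether item 1(a) covers the wait.

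Align section 10.8 and Table 7 with this wording. In section 16, report how many men in the 3-month safety denominator had no 3-month AE review.

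The cost is amendment wording, one eCRF date and at most three short calls per affected man by existing staff. No clinic visits are added, and section 10.7 already accepts telephone contact at 6 months. The change partly reverses the deliberate reduction in requirements, and AE rates may come out slightly higher because events are asked about more often.
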